## 17.2 Secondary Efficacy

### 17.2.1 Secondary Efficacy Variables & Derivations

Secondary efficacy endpoints:

$Kt/V_{urea}$ , Urea Reduction Ratio and the reduction ratios of  $\alpha 1$ -MG, YKL-40, CFD, myoglobin and  $\kappa$  FLC obtained at the mid-week treatment day dialysis session.

Derivations of analysis variables:

For this single hemodialysis treatment study,  $spKt/V_{urea}$  is adopted to calculated  $Kt/V_{urea}$ .

$SpKt/V_{urea}$  refers to single pool  $Kt/V$ . The single pool  $Kt/V$  will be calculated as:

$$spKt/V_{urea} = -\ln[(\text{post dialysis Urea})/(\text{pre dialysis Urea})] - 0.008 \times \text{total dialysis time(h)} + [4 - 3.5 \times (\text{post dialysis Urea})/(\text{pre dialysis Urea})] \times (\text{ultrafiltration volume (in liters)})/(\text{post dialysis weight})$$

Reduction ratio (unit: %) =  $(1 - \frac{C_{post}}{C_{pre}}) \times 100\%$

$C_{Pre}$  and  $C_{Post}$  are the measured arterial plasma concentrations of the solute before and after the mid-week treatment day dialysis session, respectively [3].

However, for the middle molecules ( $\kappa$  FLC,  $\alpha 1$ -MG, CFD, YKL-40, myoglobin)  $C_{Post}$  will be first corrected ( $C_{Post-corr}$ ) for the decrease in total extracellular volume due to fluid removal as follows:

$$C_{Post-corr} = \left( \frac{C_{post}}{1 + \frac{BWP_{Pre} - BW_{Post}}{0.2 \times BW_{Post}}} \right)$$

$C_{Post}$  is the measured plasma concentration of the solute after dialysis; and  $BWP_{Pre}$  and  $BW_{Post}$  are the patient's body weight before and after dialysis, respectively [4].

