## 7.1.5 Patient Selection

### 7.1.5.1 Inclusion Criteria

All of the following criteria must be met for the patient to be eligible for participation.

1. Patients aged  $\geq 18$  years old and  $\leq 80$  years old, regardless of gender;
2. Patients who are able to sign informed consent form (ICF) after an explanation of the proposed study;
3. Patients who receive in-center HD treatment at a site that routinely implements high flux dialysis and HDF;
4. Patients who have been stable receiving in-center HD/HDF for  $>3$  months prior to study enrollment;
5. Patients with kidney failure receiving maintained HD treatment with a history of thrice weekly HD, and at least 1 HDF session within 1 month prior to the study shall be judged by the investigator;
6. Patients who have an adequate arteriovenous (AV) fistula or graft, or dual-lumen tunneled catheter capable of providing a blood flow rate (QB) of at least 250 mL/min;
7. Patients have no changes in dialysis prescription (dialyzer, time, dialysis fluid flow rate (QD), QB, sufficient dialysis anticoagulation, and stable prescribed doses) over last 6 treatments as judged by the investigator. The dialysis treatment time should be 3.5 to 4.5 hours per session with minimum QB of 250 mL/min and QD of 500 mL/min;

---

8. Patients with a minimum total convective volume (including ultrafiltration (UF)) of 16 L post-dilution for the most recent HDF treatment;
9. Patients who have  $Kt/V_{urea} > 1.2$  for the last 2 measurements, with the most recent  $Kt/V_{urea}$  measurement taken within 4 weeks before or during study screening.

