### 7.1.6.2 Method for Evaluation, Recording and Analysis of Efficacy Endpoints and Time Selection

#### 7.1.6.2.1 Evaluation Methods

##### (1) Reduction ratio (RR):

The RR for each solute, based on the change in the arterial plasma concentration over the dialysis session, will be calculated as:

$$RR(\%) = (1 - \frac{C_{post}}{C_{pre}}) \times 100\%$$

Where  $C_{pre}$  and  $C_{post}$  are the measured arterial plasma concentrations of the solute before and after dialysis, respectively [17].

However, for the middle molecules ( $\lambda$  FLC,  $\kappa$  FLC,  $\alpha 1$ -MG, CFD, YKL-40, myoglobin and  $\beta 2$ -MG)  $C_{post}$  will be first corrected ( $C_{post-corr}$ ) for the decrease in total extracellular volume due to fluid removal as follows:

$$C_{post-corr} = \left( \frac{C_{post}}{1 + \frac{BW_{pre} - BW_{post}}{0.2 \times BW_{post}}} \right)$$

Where  $C_{post}$  is the measured plasma concentration of the solute after dialysis; and  $BW_{pre}$  and  $BW_{post}$  are the patient's body weight before and after dialysis, respectively [18].

(2)  $spKt/V_{urea}$  refers to single pool  $Kt/V$ . The single pool  $Kt/V$  will be calculated as [1]:

$$spKt/V_{urea} = -\ln[\frac{\text{post dialysis Urea}}{\text{pre dialysis Urea}} - 0.008 \times \text{total dialysis time(h)}] + [4 - 3.5 \times \frac{\text{post dialysis Urea}}{\text{pre dialysis Urea}}] \times$$

$$\frac{\text{ultrafiltration volume (in liters)}}{\text{post dialysis Weight}}$$

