#### **7.2.1.3 Treatment Period (mid-week session)**

**(Note: Must be conducted within 2 weeks after randomization)**

During the mid-week treatment, the patient will undergo HD/HDF treatment, according to the according to the randomization number corresponding to the treatment group. Blood samples before dialysis should be collected as baseline data for patients. See Section 7.2.3 for detailed requirements for blood sample collection. All the following visit contents need to be collected before and after dialysis except for 24-h urine protein, which needs to be collected only before dialysis.

Parameter setting of HD/HDF treatment: QB  $\geq 250$  mL/min, QD  $\geq 500$  mL/min, QR (including UF)  $\geq 16$  L, treatment time: 4 hours.

Items tested at the Clinical Lab of Research Center.

---

- 1) Blood routine: Hematocrit , hemoglobin , mean corpuscular hemoglobin , mean corpuscular hemoglobin concentration , mean corpuscular volume , platelet count, red blood cell count, white blood cell count, eosinophil percentage;
- 2) Creatinine;
- 3) Blood urea nitrogen/blood urea;
- 4) CRP;
- 5) Electrolytes: P, K, Na, Ca, Cl
- 6) Liver function: ALT, AST, GGT, bilirubin, total bilirubin, total protein, globulin, albumin;

Items need to be tested at the Central Laboratory:

- 1)  $\beta$ 2-MG;
- 2)  $\alpha$ 1-MG;
- 3)  $\lambda$  FLC;
- 4)  $\kappa$  FLC;
- 5) YKL-4;
- 6) CFD;
- 7) Myoglobin;
- 8) Serum Albumin

Other visit assessments:

- 1) Vital signs: collect vital signs pre- and post-dialysis (according to various standard operating procedures): BP, pulse: pre- and post-dialysis; breathing rate and axillary temperature: Before dialysis treatment.
- 2) Body weight, dry weight (pre- and post-dialysis) ;
- 3) Treatment parameters: Dialysis date, start time and end time of each HD/HDF treatment, dialysis machine used, name of dialyzer, dialysate type and composition (sodium, bicarbonate, A concentrate used), preset QB, QD and ultrafiltration rate (QUF) (in mL/min), preset ultrafiltration volume (in L); actual total ultrafiltration volume at the end of treatment (unit: L); additional collection in control group: The preset amount of replacement fluid and the actual amount of replacement (unit: L); during the study visit, the QB should be recorded at the beginning of treatment and if there is any adjustment during the treatment; QD (mL/min) at the end of the treatment, and total dialysis time; The duration and reason of any treatment interruption;

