### 8.2 Multiple Comparisons / Multiplicity

The two primary endpoints will be tested simultaneously. Only when both primary endpoints pass is the study declared successful. Therefore, no multiplicity adjustment are necessary for this portion. Hierarchical structure will be used for the testing for both non-inferiority and superiority. Superiority will only be tested if non-inferiority passes.

There are no other multiplicity adjustments are made for the study. The secondary endpoint is not assigned to alpha, so it not refers to alpha adjustment. All secondary endpoints, all p values are descriptive in nature only.

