### 17.2.2 Analysis Of Secondary Efficacy Variables

FAS population will be used for secondary efficacy variables.

Quantile-Quantile (Q-Q) plot will be drawn to testify the normality distribution of the

Kt/Vurea and URR. If the variable follows the normality distribution, a t-test will be used to evaluate differences between treatment groups in Kt/Vurea and URR. Otherwise, Wilcoxon Rank-Sum test will be used.

Quantile-Quantile (Q-Q) plot will be drawn to testify the normality distribution of the RRs of  $\alpha 1$ -MG, YKL-40, CFD, myoglobin and  $\kappa$  FLC. If the variable follows the normality distribution, a t-test will be used to evaluate differences between treatment groups for the RRs of  $\alpha 1$ -MG, YKL-40, CFD, myoglobin and  $\kappa$  FLC obtained at the mid-week treatment day dialysis session. Otherwise, Wilcoxon Rank-Sum test will be used.

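### SAP 17.2.1 moves the 0.008 × time term of spKt/V outside the logarithm, so Kt/V would be about 10% lower than under the protocol formula and the group difference about 9% to 13% smaller

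*SAP*

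**What the plan says.** Protocol 7.1.6.2.1 defines single-pool Kt/V with the time term inside the logarithm: "\ln[\frac{\text{post dialysis Urea}}{\text{pre dialysis Urea}} - 0.008 \times \text{total dialysis time(h", where the bracket closes only after that term. SAP 17.2.1 states that spKt/V "is adopted to calculated" Kt/V urea, and then gives "\ln[(\text{post dialysis Urea})/(\text{pre dialysis Urea})] - 0.008 \times \text{total dialysis time(h", where the logarithm has already closed after the urea ratio. The remaining part, [4 − 3.5 × urea ratio] × ultrafiltration volume / post-dialysis weight, is the same in both documents.

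Kt/V urea is listed first among the secondary endpoints in Protocol 7.1.6.1. SAP 17.2.2 compares the arms on the derived values: if they are normally distributed, "a t-test will be used to evaluate differences between treatment groups in Kt/Vurea and URR"; otherwise a Wilcoxon rank-sum test is used. SAP Section 4 lists two departures from the protocol, dropping the baseline tests and replacing LOCF. The Kt/V formula is not one of them.

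**The concern.** The two expressions are different functions, not two ways of typesetting one. Subtracting 0.008 × time inside the logarithm makes its argument smaller and so raises Kt/V. Subtracting it outside lowers Kt/V. The SAP governs the final analysis (SAP 5.3), so a programmer following it would derive every Kt/V value by a formula that conflicts with the protocol, with no record that a change was intended.

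At stake are the reported Kt/V levels and the estimated difference between the two modalities in small-solute removal. The study values would also be on a different scale from the protocol definition, which matters to anyone reading them beside the Kt/V > 1.2 entry criterion.

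**Working it through.** **Inputs from the documents.** Session time t = 4 h (Protocol 7.2.1.3: "treatment time: 4 hours"). For a range, inclusion criterion 7 in Protocol 7.1.5.1: "The dialysis treatment time should be 3.5 to 4.5 hours per session". Entry level Kt/V > 1.2 "for the last 2 measurements, with the most recent" one recent (inclusion criterion 9).

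**Assumptions.** The documents give no urea ratios, ultrafiltration volumes or weights for this endpoint, and no spKt/V result to reproduce. I take R = post/pre urea from 0.20 to 0.40, and u = ultrafiltration volume / post-dialysis weight from 0 to 0.06, with 2.5 L / 60 kg = 0.0417 as the worked case.

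**Formulas.**

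- Protocol: P = −ln(R − 0.008t) + (4 − 3.5R) × u
- SAP: S = −ln(R) − 0.008t + (4 − 3.5R) × u
- Subtracting: S − P = ln(1 − 0.008t/R) − 0.008t. This is always negative and does not depend on u.

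**One case in full** (R = 0.25, t = 4, so 0.008t = 0.032):

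- P = −ln(0.218) + 3.125 × 0.0417 = 1.523 + 0.130 = 1.653
- S = −ln(0.25) − 0.032 + 0.130 = 1.386 − 0.032 + 0.130 = 1.485 (unrounded 1.4845)
- S − P = −0.169, or −10.2%

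**Level at t = 4 h, u = 2.5/60:**

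| R | Protocol | SAP | Difference | Relative |
|---|---|---|---|---|
| 0.20 | 1.921 | 1.715 | −0.206 | −10.7% |
| 0.25 | 1.653 | 1.485 | −0.169 | −10.2% |
| 0.30 | 1.440 | 1.295 | −0.145 | −10.1% |
| 0.35 | 1.261 | 1.133 | −0.128 | −10.1% |

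At 4 h over the full grid (R 0.20 to 0.40, u 0 to 0.06), the SAP value is 9.7% to 11.6% lower, or 0.115 to 0.206 units. At u = 0.04 it is 8.9% to 9.5% lower at 3.5 h and 11.3% to 12.1% lower at 4.5 h.

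**At the entry level.** A patient at exactly 1.20 by the protocol formula (t = 4 h) has R = 0.333 if u = 0 and R = 0.368 if u = 0.04. The SAP formula returns 1.067 and 1.077.

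**Group difference at t = 4 h, u = 0.04:**

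| R in the two groups | Protocol | SAP | Change |
|---|---|---|---|
| 0.25 vs 0.22 | 0.152 | 0.132 | −13.3% |
| 0.30 vs 0.27 | 0.123 | 0.110 | −10.9% |
| 0.35 vs 0.30 | 0.178 | 0.161 | −9.5% |

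**Effect of time at R = 0.25.** Going from 3.5 to 4.5 h changes P by −ln(0.214) + ln(0.222) = +0.037, and S by −0.008.

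**Effect on the test.** I simulated 5,000 trials of 136 per arm (assumed mean R 0.28 vs 0.265, SD 0.05; u about 0.04; t about 4 h). The mean difference was 0.067 by the protocol formula and 0.059 by the SAP formula. The mean t statistics were 2.405 and 2.399. The verdict at p < 0.05 differed in 1% of runs.

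**The case against.** The strongest reply is that no decision depends on this. SAP 8.2 assigns no alpha to the secondary endpoints: "All secondary endpoints, all p values are descriptive in nature only". Trial success rests on the λ FLC and β2-MG reduction ratios, and neither uses the formula. Sample size, re-estimation, safety and URR are also untouched. Because the spread shrinks almost in step with the difference, the test result barely moves. All of this stands. It limits the consequence to the reported levels and effect size. With descriptive p values, though, those estimates are what a reader will use.

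Two other points also have some force:

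- **Time.** The sign reversal matters little when sessions run to plan. Post-dialysis sampling is set at 240 ± 5 minutes, and 5 minutes at R = 0.25 moves Kt/V by about 0.003 (protocol) or 0.0007 (SAP). It matters more for sessions that stop early, which may be sampled from 210 minutes and stay in the FAS.
- **Entry criterion.** The SAP derivation does not decide eligibility, and no planned analysis compares study-session Kt/V with 1.2. The effect there is on interpretation only.

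Two doubts concern the source. The SAP says it is based on protocol V1.0, whose formula is not available here. However, the SAP is dated 28 June 2022, after protocol V1.1 of 30 May 2022, and it conflicts with that version. The difference also turns on one bracket in an equation extracted from PDF, so the signed PDF is worth a glance. As they stand, both expressions are well formed with balanced brackets, and nothing in the text points to a misreading.

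**Conclusion.** The concern holds, and the SAP formula is wrong as written. It contradicts the protocol on a named secondary endpoint, and the change is not declared. Relative to the protocol definition, Kt/V would be about 10% too low (8.9% to 12.1% over the ranges tried), and the group difference about 9% to 13% too small in the examples. These percentages rest on assumed urea ratios and ultrafiltration fractions, but they vary little across plausible values, and the direction never changes. The reference is the protocol formula; the source it cites was not available to check. The harm is misreported means and effect size for one secondary endpoint, with no threat to the primary conclusion.

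**What to change.** Correct SAP 17.2.1 to match Protocol 7.1.6.2.1:

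spKt/V = −ln[(post urea / pre urea) − 0.008 × t(h)] + [4 − 3.5 × (post urea / pre urea)] × UF(L) / post-dialysis weight(kg).

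Make the same correction in the programming specification, and check the derivation program against one hand-worked patient; the R = 0.25 case above (1.653) would serve. If the SAP form was intended, declare and justify it in SAP Section 4 instead.

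The cost is a one-line SAP correction before database lock. It needs no new data, no design change and no change to the sample size.

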### 17.2.2 Analysis Of Secondary Efficacy Variables

FAS population will be used for secondary efficacy variables.

Quantile-Quantile (Q-Q) plot will be drawn to testify the normality distribution of the

Kt/Vurea and URR. If the variable follows the normality distribution, a t-test will be used to evaluate differences between treatment groups in Kt/Vurea and URR. Otherwise, Wilcoxon Rank-Sum test will be used.

Quantile-Quantile (Q-Q) plot will be drawn to testify the normality distribution of the RRs of  $\alpha 1$ -MG, YKL-40, CFD, myoglobin and  $\kappa$  FLC. If the variable follows the normality distribution, a t-test will be used to evaluate differences between treatment groups for the RRs of  $\alpha 1$ -MG, YKL-40, CFD, myoglobin and  $\kappa$  FLC obtained at the mid-week treatment day dialysis session. Otherwise, Wilcoxon Rank-Sum test will be used.

## **18 Safety Analysis**

All outputs for safety outcomes will be based on safety set, and presented by treatment groups.

### **18.1 Treatment parameters**

Treatment parameter will be presented for safety set and be summarized by treatment and categories. A listing will be provided.

The following treatment parameter will be reported for this study:

- Total dialysis time(min)
- Programmed QB(mL/min)
- Programmed QUF(mL/min)
- QB adjusted during the dialysis treatment
- Type of vascular access
- Treatment type
- Dialysate type
- Scheduled replacement volume (L)
- Actual replacement volume (L)
- Treatment interruption, interruption time will also be summarized when treatment interruption exists.
- Anticoagulation type
- Anticoagulation supplement during the treatment, total supplement dose will also be summarized when anticoagulation supplement during the treatment exist.

- Dry weight(kg)

## 18.2 Adverse Events

An AE is any untoward medical occurrence in a clinical study and which does not necessarily have to have a causal relationship with the investigational medical device *Chinese medical device GCP Article 93*. Adverse Events (AEs) will be coded using MedDRA and presented by System Organ Class (SOC) and Preferred Term (PT). Treatment-emergent AE (TEAE) will include AEs that occur on the day of or after the study treatment and will be summarized in the safety summaries. Pre-treatment AEs including AEs reported at Screening and Randomization will be recorded in the eCRF but will not be summarized in the safety summaries.

In AE summaries, the primary system organ class will be presented alphabetically and the preferred terms will be sorted within primary SOC in descending frequency. The sort order for the preferred term will be based on their frequency. Treatment group comparability in the incidence of AEs will be evaluated using Fisher's exact test.

### Severity of AE

Severity is classed as mild/ moderate/ severe. If severity is missing, the AE will be considered severe.

### Relationship with Study Device/ Study Procedure

Relationship, as indicated by the Investigator, is classed as “Unable to Judge”, “Definitely Unrelated”, “Possibly Unrelated”, “Possibly Related”, “Probably Related”, “Definitely Related” (increasing severity of relationship).

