**Table 3. Causality Assessment \***

	treatment methods. The AE is resolved when the disease status is improved or other treatment methods are stopped. The AE occurs when other treatment methods are reused.	
Unable to Judge	It cannot be assessed with the above rationale.	YES

\*Causality assessment based on the Chinese medical device GCP

Causality: Performed by a medical professional and is a determination of whether there is a reasonable possibility that a medical device/procedure is etiologically related to/associated with an AE. Causality assessment includes, for example, assessment of temporal relationships, underlying disease, presence (or absence) of a more likely cause, and physiologic plausibility. Investigator shall provide an alternative etiology for SAEs that are definitely unrelated or possibly unrelated to use of study medical device. If the alternative etiology is unknown, investigator shall document “unknown.”

For AEs with causal relationship (Definitely Related, Probably Related, Possibly Related or Unable to Judge) to Theranova 400, the AE must also be reported as a device deficiency to the Sponsor.

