### Relationship with Study Device

Treatment-related AE is defined as a AE with a relationship as “Possibly Related”, “Probably Related” or “Definitely Related” or “Unable to Judge” to the study treatment. AEs with a missing relationship to study treatment will be regarded as “Definitely Related” to study treatment. If a patient reports the same AE more than once within that SOC/ PT, the AE with the worst-case relationship to study medication will be used in the corresponding relationship summaries.

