### Relationship with study procedure

AEs related to study procedure is defined as a AE with a relationship to the study procedure as “possibly related”, “probably related” or “definitely related” or “unable to judge” to study procedure. If a patient reports the same AE more than once within that SOC/ PT, the AE with the worst-case relationship to study medication will be used in the corresponding relationship summaries.

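### The SAP's relationship scale ranks Unable to Judge below both unrelated grades although it counts as related, so the worst-case rule can keep an unrelated rating for a repeated event

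*SAP*

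**What the plan says.** Four statements bear on the point.

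- **The scale.** SAP 18.2, under the heading covering both device and procedure, says that relationship is "classed as “Unable to Judge”, “Definitely Unrelated”, “Possibly Unrelated”, “Possibly Related”, “Probably Related”, “Definitely Related” (increasing severity of relationship"). Read as a ranking, as the label "increasing severity of relationship" directs, Unable to Judge is the lowest grade.
- **What counts as related.** The next subsection defines a treatment-related event. Its list of qualifying grades ends with "Definitely Related” or “Unable to Judge” to the study treatment". The procedure subsection does the same: "or “unable to judge” to study procedure".
- **The collapse rule.** "If a patient reports the same AE more than once within that SOC/ PT", then "the AE with the worst-case relationship to study medication will be used in the corresponding relationship summaries". The procedure subsection repeats the rule.
- **The protocol.** Table 3 in Protocol 13.1.2 marks Unable to Judge as having a causal association. The note below it names the causal grades as "Definitely Related, Probably Related, Possibly Related or Unable to Judge".

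The outputs that could use these rules are the treatment-related and procedure-related rows of the overview table (SAP 18.2.1), the treatment-related tables (SAP 18.2.3, 18.2.5, 18.2.7 and 18.2.9) and the table by severity and relationship to the dialyzer planned in Protocol 8.7.1.3.

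**The concern.** The worst-case rule is meant to be cautious: when a patient's ratings for one term differ, the most incriminating one should stand. That works only if every related grade ranks above every unrelated grade. Here one related grade sits at the bottom, so the rule can discard a record that meets the SAP's definition of related in favour of one that does not.

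This goes against the rest of the section. For the device, "AEs with a missing relationship to study treatment will be regarded as “Definitely Related” to study treatment", and a missing severity is set to severe. A blank relationship field is thus handled more cautiously than an investigator's explicit statement that the relationship cannot be judged.

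At stake is the related-event count by patient and term. There is also a possible mismatch with safety reporting. Protocol 13.1.2 requires an Unable to Judge event on Theranova 400 to be reported to the sponsor as a device deficiency as well. The same patient and term could then appear as unrelated in a summary table.

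**Working it through.** The documents give no figure to reproduce. The check is logical: apply the rule to every mix of grades that one patient could have for one term.

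**Inputs**

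| Grade | Rank in SAP 18.2 | Related under SAP 18.2 and Protocol Table 3? |
|---|---|---|
| Unable to Judge | 1 | Yes |
| Definitely Unrelated | 2 | No |
| Possibly Unrelated | 3 | No |
| Possibly Related | 4 | Yes |
| Probably Related | 5 | Yes |
| Definitely Related | 6 | Yes |

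**Rule.** Retained grade = the highest rank among the patient's records for that term. A mix is misclassified if it contains a grade from {1, 4, 5, 6} but the retained grade is 2 or 3.

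**Which mixes fail.** For the highest rank to be 2 or 3, no record may have rank 4, 5 or 6. For the mix still to contain a related grade, rank 1 must be present. The failing mixes are therefore rank 1 with rank 2, rank 3 or both: 2² − 1 = 3 mixes.

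- Two different grades: C(6,2) = 15 mixes, 2 fail. Unable to Judge with Definitely Unrelated is kept as Definitely Unrelated. Unable to Judge with Possibly Unrelated is kept as Possibly Unrelated.
- Three different grades: C(6,3) = 20 mixes, 1 fails. Unable to Judge with both unrelated grades is kept as Possibly Unrelated.
- Four or more different grades: none fail, because at least one of ranks 4 to 6 must be present.

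**Opposite direction.** A mix with no related grade contains only ranks 2 and 3, so it stays unrelated. No mix moves from unrelated to related.

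**When it reaches a table.** Take a patient with one term recorded twice, once Unable to Judge and once Definitely Unrelated.

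- Select related events, then collapse: the Unable to Judge record is selected and the patient counts as related. No error.
- Collapse, then select: Definitely Unrelated is kept and is not selected. The patient does not count as related.
- Table by relationship grade: the patient and term appears under Definitely Unrelated.

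The SAP does not say which of the first two sequences applies.

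**After correction.** With Unable to Judge ranked just below Possibly Related, or at the top of the scale, 0 of 15 pairs and 0 of 20 triples are misclassified.

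**The case against.** The strongest reply is that the ranking may never come into play. The SAP defines a treatment-related event record by record, and the treatment-related outputs it names are subsets under that definition. If events are selected first, the Unable to Judge record survives. A table split by relationship grade, where the ranking acts directly, is not among the outputs in SAP 18.2.1 to 18.2.9; only Protocol 8.7.1.3 plans one, and only for the dialyzer. SAP 9 also gives the table templates priority over the SAP text. The templates are not available here and might set another order.

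This makes the harm conditional. It does not remove it: the sequence of selection and collapse is unstated, a table by relationship is planned in the protocol, and the SAP text offers no other order for deciding the worst case.

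The trigger is also rare. There is one study session, with adverse events reviewed at the next one (Protocol 7.2.1.4), and an event that changes in severity is recorded only once (Protocol 13.1.2). For the device, a missing rating goes to the top of the scale and so prevents the error. All of this stands, and it keeps the point minor.

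A reader might infer three stronger things, which the documents do not support:

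- *Every such patient is certainly misclassified.* Not if related events are selected before the collapse.
- *The error appears in both the device and the procedure results.* The two relationships are rated separately, so mixed ratings on one do not imply mixed ratings on the other. The SAP names only an overview row for procedure.
- *The undercount favours Theranova, because investigators would be less sure about a new device.* Neither document gives rating frequencies by arm, and the error also needs an unrelated rating for the same term in the same patient. No direction by arm follows.

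**Conclusion.** The scale is wrong as written: it contradicts the definitions of related events in the same SAP section and in Protocol Table 3. Three mixes of grades are affected, all moving from related to unrelated.

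The consequence is limited to one patient-by-term cell at a time, in summary tables only. It requires a repeated term with one record Unable to Judge, the others unrelated and none in the three explicitly related grades. It also requires either collapse before selection or a table by relationship grade. A single Unable to Judge event still counts as related, and individual ratings remain visible in the listings. The documents give no rate of repeated or mixed ratings, so the number of patients cannot be computed; with one session it is probably small. No efficacy result is touched.

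The conclusion assumes that the worst case is taken from the stated scale and that the templates do not override it.

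**What to change.** In SAP 18.2, for both device and procedure, do one of the following:

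- rank Unable to Judge above Possibly Unrelated, for example: Definitely Unrelated < Possibly Unrelated < Unable to Judge < Possibly Related < Probably Related < Definitely Related; or
- state that a patient and preferred term counts as related if any record meets the SAP's definition of related.

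The exact place above Possibly Unrelated does not matter for the related/unrelated split. The second option also makes that split independent of the order of selection and collapse, though a table by relationship grade would still need a corrected ranking. Align the table templates, since they take priority.

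The same edit can tidy two neighbouring points. The collapse rule speaks of study medication in both subsections, where device and procedure are meant. The procedure subsection also has no rule for a missing relationship.

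The cost is one line in the SAP and a check of the templates before database lock, with no new data and no change to the efficacy analysis.
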